9.3 Prohibited Medications

Medications that are prohibited in this study (Screening Period through the Safety Follow-up Visit) are shown in Table 9-1. VX-440, TEZ, and IVA are metabolized extensively via CYP3A4. VX-440 is also metabolized extensively by CYP2C9 and to a lesser extent by CYP2C19. Therefore, the use of moderate and strong inducers of CYP3A or CYP2C9 and strong and moderate inhibitors of CYP3A, which have the potential to alter the exposure of VX-440, TEZ, or IVA, will be restricted in this study. Preliminary results from Study 002 indicate that VX-440 is a moderate to strong inducer of CYP3A4 at higher doses; therefore, sensitive CYP3A substrates with a narrow therapeutic index should be used with caution during the study. VX-440 was shown in vitro to be an inhibitor of the hepatic transporter organic anion transporting polypeptide 1B1 (OATP1B1). Therefore, sensitive substrates of OATP1B1, such as HMG Co-A Reductase Inhibitors (i.e., “statins”), are restricted during treatment with VX-440 or placebo. As VX-440 has demonstrated the potential for inhibition of CYP2C9 in vitro, warfarin is also prohibited during treatment with VX-440 or placebo.

A non-exhaustive list of study prohibitions and cautions for medication will be provided in the Study Reference Manual.

Table 9-1 Prohibited Medications

Medication	Timing of Restriction	
	Start of Restriction	End of Restriction
Moderate and strong CYP3A or CYP2C9 inducers	None allowed within 14 days before the first dose of the study drug on Day 1 (Parts 1 [REDACTED] or Day -28 (Part 2)	None allowed through the Safety Follow-up Visit
Moderate and strong CYP3A inhibitors (except ciprofloxacin)	None allowed within 14 days before the first dose of the study drug on Day 1 (Parts 1 [REDACTED] or Day -28 (Part 2)	None allowed through the Safety Follow-up Visit
Sensitive OATP1B1 substrates	None allowed within 14 days before the first dose of VX-440 or placebo on Day 1	None allowed until after last dose of VX-440 or placebo
Warfarin	None allowed within 14 days before the first dose of VX-440 or placebo on Day 1	None allowed until after last dose of VX-440 or placebo
Commercially available CFTR modulators (e.g., Kalydeco, Orkambi)	Parts 1 [REDACTED] None allowed within 14 days before screening Part 2 : None allowed from the start of the Run-in Period	Parts 1 [REDACTED] None allowed through the Safety Follow-up Visit Part 2 : None allowed through end of the Washout Period

CFTR: Cystic fibrosis transmembrane conductance regulator; CYP: cytochrome P450; OATP1B1: organic anion transporting polypeptide 1B1

Note: The use of restricted medication by subjects with medical needs will be addressed on a case-by-case basis with the medical monitor.

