In vitro data indicate that maintaining adequate IVA exposure in vivo will be important for maximizing efficacy of the TC. When administered in combination with VX-440 200 mg, the dose of IVA will be the same as the recommended dose for IVA monotherapy for patients aged 12 years and older (150 mg q12h). Preliminary data from Study 002 indicate that VX-440 is a moderate to strong inducer of CYP3A4. Because IVA is a sensitive CYP3A substrate, the dose of IVA will be increased from 150 mg q12h to 300 mg q12h when it is administered with VX-440 at a dose level of 600 mg q12h. These dose levels were evaluated in Study 002 and were safe and well tolerated. At these dose levels, IVA exposure was approximately 50% lower relative to IVA 150 mg q12h monotherapy based on historical data.¹² If the high dose of VX-440 is reduced to 400 mg q12h, the IVA dose will remain 300 mg q12h, as VX-440 induction is predicted to be similar in magnitude at this dose relative to 600 mg q12h. Phase 3 and post-approval data for IVA monotherapy have not revealed any systemic exposure-related safety findings and indicate a wide therapeutic margin for safety. Use of a higher IVA dose when coadministering IVA with a CYP3A inducer is consistent with the approach for combination therapy with LUM (a strong CYP3A inducer). In that combination therapy, the IVA dose is 250 mg q12h.

Treatment Duration

The 4-week treatment duration in Parts 1 and 2 is based on previous experience with CF correctors and potentiators in clinical studies of subjects with CF. Based on preliminary data from Studies 001 and 002, and data from previous studies of TEZ and IVA, all components of the TC reach steady-state levels of exposure by 2 to 3 weeks. In previous studies of TEZ and IVA, PD effects were observed within 4 weeks of treatment. In Study VX06-770-101, treatment with IVA for 28 days resulted in statistically significant within-group changes from baseline in ppFEV₁ as well as a trend toward clinically meaningful improvements in the respiratory domain of the CFQ-R; differences in biomarkers of CFTR activity (sweat chloride) between IVA and placebo groups were also demonstrated. Furthermore, in Study VX11-661-101 dose-dependent

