9.2 Exclusion Criteria

1. History of any comorbidity that, in the opinion of the investigator, might confound the results of the study or pose an additional risk in administering study drug to the subject.
2. History of cirrhosis with portal hypertension.
3. Risk factors for Torsade de Pointes, including but not limited to, history of any of the following: familial long QT syndrome, chronic hypokalemia, heart failure, left ventricular hypertrophy, chronic bradycardia, myocardial infarction, cardiomyopathy, history of arrhythmia (ventricular or atrial fibrillation), obesity, acute neurologic events (subarachnoid hemorrhage, intracranial hemorrhage, cerebrovascular accident, or intracranial trauma), or autonomic neuropathy.
4. History of hemolysis.
5. G6PD deficiency, defined as G6PD activity less than the lower limit of normal (LLN) or 70% of the mean of the LLN and the ULN, whichever is greater.
6. Any of the following abnormal laboratory values at screening:
 - Hemoglobin <10 g/dL
 - Total bilirubin $\geq 2 \times$ ULN
 - Aspartate aminotransferase (AST), alanine aminotransferase (ALT), gamma-glutamyl transpeptidase (GGT), or alkaline phosphatase (ALP) $\geq 3 \times$ ULN
 - Abnormal renal function defined as glomerular filtration rate ≤ 50 mL/min/1.73 m² (calculated by the Modification of Diet in Renal Disease Study Equation)^{14, 15} for subjects ≥ 18 years of age and ≤ 45 mL/min/1.73 m² (calculated by the Counahan-Barratt equation)¹⁶ for subjects aged 12 to 17 years (inclusive)
7. An acute upper or lower respiratory infection, pulmonary exacerbation, or changes in therapy (including antibiotics) for pulmonary disease within 28 days before the first dose of study drug (Day 1 for Parts 1 [REDACTED] Day -28 for Part 2).
8. Lung infection with organisms associated with a more rapid decline in pulmonary status (e.g., *Burkholderia cenocepacia*, *Burkholderia dolosa*, and *Mycobacterium abscessus*). For subjects who have had a history of a positive culture in the past, the investigator will apply the following criteria to establish whether the subject is free of infection with such organisms:
 - The subject has had 2 respiratory tract cultures negative for these organisms within the past 12 months, with no subsequent positive cultures.
 - These 2 respiratory tract cultures were separated by at least 3 months, and 1 of them was obtained within the past 6 months.

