Follicle-stimulating Hormone (Screening Period only): Blood sample for FSH will be measured for any suspected postmenopausal female with at least 12 months of continuous spontaneous amenorrhea. Serum FSH levels must be within the postmenopausal reference range of the performing laboratory to be considered postmenopausal.

CFTR genotype (Screening Period only): CFTR genotyping will be performed for all subjects. If the screening CFTR genotype result is not received before randomization, a previous CFTR genotype laboratory report may be used to establish eligibility. Subjects who have been randomized and whose screening genotype does not confirm study eligibility must be discontinued from the study (Section 9.5).

G6PD Activity Test (Screening Period only): A single blood sample will be collected for the G6PD activity test, which will be performed in an established laboratory that runs the assay routinely.

Additional Evaluations: Additional clinical laboratory evaluations will be performed at other times if judged to be clinically appropriate.

For purposes of study conduct, only laboratory tests done in the central laboratory may be used. Local laboratories may be used at the discretion of the local investigator for management of urgent medical issues. If a local laboratory test value is found to be abnormal and clinically significant, it will be verified by the central laboratory as soon as possible after the investigator becomes aware of the abnormal result. If it is not possible to send a timely specimen to the central laboratory (e.g., the subject was hospitalized elsewhere), the investigator may base the assessment of an AE on the local laboratory value.

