13.1.1.3 Documentation of Adverse Events

All AEs will be collected from the time ICF is signed until the following time points:

- For subjects who do not enroll: until time of screen failure (e.g., screen failure, withdrawal of consent)

- For enrolled subjects who have a Safety Follow-up Visit: through the Safety Follow-up Visit
- For enrolled subjects who do not have a Safety Follow-up Visit, the earliest of
 - o 28 days after the last dose of study drug, or
 - o the ETT Visit, if that visit is 3 weeks or later following the last dose of study drug (see [Section 8.1.6](#)).

All subjects will be queried, using nonleading questions, about the occurrence of AEs at each study visit. When possible, a constellation of signs and/or symptoms will be identified as 1 overall event or diagnosis. All AEs for enrolled subjects will be recorded in the CRF and source document. AEs for subjects who are screened but not subsequently enrolled in the study will be recorded only in the subject's source documents. The following data will be documented for each AE:

- Description of the event
- Classification of “serious” or “nonserious”
- Date of first occurrence and date of resolution (if applicable)
- Severity
- Causal relationship to study drug(s)
- Action taken
- Outcome
- Concomitant medication or other treatment given

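### Minor, optional: Table 9-1 lets a paused statin or warfarin restart straight after the Day 29 dose, while VX-440 is still at steady-state exposure, and the Section 9.3 lead-in conflicts with those rows

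*Protocol*

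**What the plan says.** Protocol Section 9.3 gives VX-440 itself as the reason for both restrictions. It inhibits the hepatic transporter OATP1B1 in vitro, so sensitive substrates such as statins "are restricted during treatment with VX-440 or placebo". It may also inhibit CYP2C9, again on in vitro data, so warfarin is barred for the same period.

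In Table 9-1 both restrictions start 14 days before the first VX-440 or placebo dose on Day 1, and both end with "None allowed until after last dose of VX-440 or placebo". The schedules of assessments (Tables 3-1 to 3-3) put that last dose on the morning of Day 29 in Parts 1 and 2.

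Other text bears on the point:

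- The opening sentence of Section 9.3 gives one general period for everything in Table 9-1, from screening to the Safety Follow-up Visit. That is longer than these two rows allow.
- Section 8.2.2 states that "all components of the TC reach steady-state levels of exposure by 2 to 3 weeks", and Section 10.2 sets 12-hourly dosing.
- Section 9.3 adds: "A non-exhaustive list of study prohibitions and cautions for medication will be provided in the Study Reference Manual". That manual is not among the documents.

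**The concern.** A restriction that exists because VX-440 is an inhibitor should last as long as a relevant amount of VX-440 is present. These rows require 14 clear days before Day 1, when the subject has taken no VX-440 in the Treatment Period, and no clear time after Day 29, when exposure is at its on-treatment level. A subject who had paused a statin or warfarin could restart on the afternoon of Day 29 and comply with the table.

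What is at stake is the safety of individual subjects: possible raised statin exposure or excess anticoagulation for a short time. Efficacy, power and type I error are not involved, because the Day 29 assessments are scheduled before that dose.

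**Working it through.** The plan gives no figure to reproduce. The check compares passages and adds some simple arithmetic.

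**1. Exposure when the restriction ends.** Dosing starts on Day 1, so the Day 29 morning dose falls 29 − 1 = 28 days later. Steady state is stated to be reached by 14 to 21 days, which is earlier. With 12-hourly dosing, the 12 hours after the Day 29 dose match any other steady-state dosing interval. This needs no half-life; it assumes only that the subject dosed as planned.

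**2. Does other text close the gap?**

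- *Section 9.3 lead-in.* Read alone, it would carry the prohibition to Safety Follow-up. The row-specific end dates and the body sentences on treatment with VX-440 or placebo set the shorter period. The text conflicts with itself.
- *Table 9-1 note.* The medical monitor decides case by case on restricted medication. After the last dose these drugs are no longer restricted.
- *Section 9.4.* Starting new long-term medication needs approval up to Safety Follow-up. A resumed drug is not clearly new.
- *Exclusion 16.* It covers only the period before dosing.

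**3. How many subjects.** Planned VX-440 recipients, from Table 8-2 ratios:

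- Cohort 1A: 10 × 4/5 = 8
- Cohort 1B: 32 × 3/4 = 24
- Part 2: 24 × 3/4 = 18
- Total: 50 of 10 + 32 + 24 = 66

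The number of statin or warfarin users is not given. If 0% to 4% is assumed, the count is 0 to 2 of 50.

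**4. Amount of VX-440 left (illustration only).** The documents give no VX-440 half-life. Assume first-order linear kinetics and 4 to 5 half-lives to steady state. The stated 2 to 3 weeks then gives an upper limit on the half-life between 14/5 = 2.8 and 21/4 = 5.25 days. The lower end, 0.5 day, is assumed. Fraction left = 2^(−t / half-life):

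| Assumed half-life (days) | Left at 12 hours | Left at 7 days |
|---|---|---|
| 0.5 | 50% | <0.1% |
| 1 | 71% | 0.8% |
| 2.8 | 88% | 18% |
| 5.25 | 94% | 40% |

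Seven days leaves 10% or less if the half-life is at most 7 / log2(10) = 2.1 days. The stated 2 to 3 weeks covers all three components, so the slowest may not be VX-440.

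**5. Length of the pause.**

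- Part 1: 14 + 28 = 42 days now, and 42 + 7 = 49 days with a 7-day interval. The ±2-day window on Day 29 gives 40 to 44 and 47 to 51.
- Part 2: the same if Table 9-1 governs. Exclusion 16, however, counts the window from Day −28. If it governs, the pause is 14 + 28 + 28 = 70 days now and 77 with 7 more.

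**6. Scheduled monitoring after Day 29.** Serum chemistry, including ALT and AST, is scheduled at Day 43, at Day 57 in Part 2, and at Safety Follow-up. After Day 29, the next scheduled coagulation test, which includes INR, is at Safety Follow-up. SAP Appendix B targets that visit at Day 57 in Part 1 and Day 85 in Part 2. Part 2 subjects who re-enter Study 661-110 after Day 57 have no such visit (Protocol Section 8.1.5).

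**The case against.** The strongest reply is that the rule covers four weeks of co-administration and that only a declining tail remains after the final dose. The table sets the earliest permitted restart; it does not direct one, and the treating physician still decides. This stands in part: for the first 12 hours exposure is not yet a tail, but after that its size and relevance are unknown.

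Very few subjects are likely to be concerned. Exclusion 1 covers "History of any comorbidity that, in the opinion of the investigator, might confound the results of the study or pose an additional risk", and Exclusion 3 lists "history of arrhythmia (ventricular or atrial fibrillation), obesity, acute neurologic events", which removes many likely users of these drugs. This stands.

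Safeguards exist. Besides the scheduled tests, Section 11.7.2 says "Additional clinical laboratory evaluations will be performed at other times if judged to be clinically appropriate", and subjects are asked "about the occurrence of AEs at each study visit". This stands too, so a reader should not infer that subjects are unmonitored after Day 29. The weak spot is INR, for which no early test is scheduled.

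A reader might take the 40% or 94% in the illustration as evidence of a substantial continuing interaction. The documents do not support that. They give no half-life, inhibition constant or in vivo interaction result. VX-440 is extensively metabolised by CYP3A4 and also induces it, so the time to steady state may reflect induction rather than half-life, and the upper figures may be well above the truth.

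A reader might also infer that warfarin should be withheld for a further week. That would exchange a definite longer time without anticoagulation for protection against an in vitro signal of unknown size. Because of the blind, it would also fall on the 66 − 50 = 16 subjects not given VX-440. Leaving the warfarin pause unextended is a defensible choice.

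**Conclusion.** The end of the restriction in both rows does not fit its stated reason, whatever the VX-440 half-life, and the Section 9.3 lead-in conflicts with the rows. This is a minor safety-wording point of optional priority. It may affect no subject at all; the 0 to 2 of 50 rests on an assumed rate of use.

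The conclusion for the first 12 hours rests on the stated steady state and 12-hourly dosing. The length of any interval needed after that cannot be derived from the documents. Nor do they show that a clinical interaction would occur, because the evidence cited is in vitro. The Study Reference Manual may already give advice on this.

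**What to change.** **OATP1B1 row.** Change the end of restriction to: *not permitted until 7 days have passed since the final VX-440 or placebo dose; this includes restarting a paused drug*. Seven days is the post-dose interval already used for contraception in Table 11-3. It was not set for this purpose, so clinical pharmacology should confirm or replace it against VX-440 PK before the text is final.

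**Warfarin row.** Do not impose a fixed longer pause. Require that any restart within that interval be agreed with the medical monitor and accompanied by INR monitoring.

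**Section 9.3 text.** Reconcile the lead-in and the sentences on the treatment period with the revised rows. Also settle whether the Part 2 window for these two classes starts from Day 1 (Table 9-1) or Day −28 (Exclusion 16).

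**Cost.** A few lines of text, and about one more week off statin: 49 days instead of 42 in Part 1, or 77 instead of 70 in Part 2 if Exclusion 16 governs. The interval ends on Day 29 + 7 = Day 36, before the Day 43 Visit, so the statin change adds no scheduled visit. A warfarin user who restarts early would need unscheduled INR tests, which Section 11.7.2 already permits.

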9.4 Prior and Concomitant Medications

Information regarding all prior and concomitant medications, including the subject's CF medications, other medications, and herbal and naturopathic remedies administered from 28 days before the Screening Visit through the Safety Follow-up Visit, if applicable, will be recorded in each subject's source documents. For subjects who are screened but are not subsequently randomized in the study, details of prior medication will only be documented in the subjects' source documents.

- Subjects must remain on a stable medication (and supplement) regimen for their CF from 28 days before Day 1 through the Safety Follow-up Visit. Stable medication regimen is defined as the current medication regimen for CF that subjects have been following for at least 28 days before Day 1. Subjects must not initiate long-term treatment with new medication from 28 days before Day 1 through the Safety Follow-up Visit unless discussed and approved by the medical monitor. Guidelines for stable medication regimens for CF are as follows:
 - Subjects who are taking daily inhaled tobramycin or other chronically inhaled antibiotics should remain on that regimen throughout the study.
 - Subjects who cycle onto and off of an inhaled antibiotic should continue on their prior schedule. The timing of the first dose of study drug on Day 1 should be synchronized as closely as possible (and not more than ± 3 days) to the first day in the cycle onto the inhaled antibiotic.
 - Subjects who alternate between 2 different inhaled antibiotics should remain on the same cycling schedule during the study. The timing of the first dose of study drug on Day 1 should be synchronized as closely as possible (and not more than ± 3 days) to the first day in the cycle onto 1 of the inhaled antibiotics.
- Subjects may receive doses of prednisone of up to 10 mg/day or equivalent (chronically) or prednisone 60 mg qd for up to 5 days without prior approval of the medical monitor.
- Information about bronchodilator use during the study will be collected and documented. Subjects who are using a bronchodilator must have their spirometry assessments performed according to the guidelines provided in [Section 11.6.1](#).

9.5 Removal of Subjects

Subjects may withdraw from the study at any time at their own request. Subjects may be withdrawn from study drug treatment at any time at the discretion of the investigator or Vertex for safety, behavior, noncompliance with study procedures, or administrative reasons. If a subject has been withdrawn from study drug treatment, the subject will continue to be followed, provided the subject has not withdrawn consent.

Subjects who have been randomized and whose screening *CFTR* genotype does not confirm study eligibility must be discontinued from the study, even if a previous *CFTR* genotype laboratory report was used to establish eligibility.

If a subject does not return for a scheduled visit, reasonable effort will be made to contact the subject. In any circumstance, reasonable effort will be made to document subject outcome. The investigator will inquire about the reason for withdrawal, request that the subject return all unused investigational product(s), request that the subject return for a Safety Follow-up Visit, if applicable (see [Section 8.1.6](#)), and follow up with the subject regarding any unresolved AEs.

If the subject withdraws consent for the study, no further evaluations will be performed and no additional data will be collected. Vertex may retain and continue to use any data collected before such withdrawal of consent.

9.6 Replacement of Subjects

Subjects who withdraw or are withdrawn before the first dose of study drug on Day 1 may be replaced.

Subjects who withdraw or are withdrawn for nonsafety reasons during the study drug treatment period may be replaced at Vertex's discretion.

10 STUDY DRUG ADMINISTRATION AND MANAGEMENT

Study drug refers to VX-440, TEZ/IVA, TEZ, IVA, and their matching placebos.

10.1 Preparation and Dispensing

Study drug may be dispensed only under the supervision of the investigator or an authorized designee and only for administration to the study subjects.

10.2 Administration

Study drug will be administered orally. Subjects will receive the same number of tablets each day to maintain the blind. Additional information is provided in the Pharmacy Manual.

Study drug will be administered with a fat-containing meal or snack, such as a standard "CF" high-fat, high-calorie meal or snack or a standard meal, according to the following guidelines:

1. It is recommended that the dose be taken within 30 minutes of the start of the meal or snack.
2. Study drug will be administered q12h (\pm 2 hours). For each subject, all doses of study drugs will be taken at approximately the same time each day. For example, the morning dose could be taken at 08:00 every morning and the evening dose could be taken at 20:00 every evening throughout the study.
3. The date, amount taken, and time of study drug administration, including whether food was taken with each dose, will be recorded for the 2 doses before PK sample collection and the dose received on the morning of PK sample collection.
4. On days of scheduled visits, the morning dose of study drug will be administered at the site after predose assessments have been completed. The meal or snack will be provided by the site for the morning dose of study drug.

5. If a subject's scheduled visit is to occur in the afternoon, the following guidelines must be used:
 - If the dose in the clinic will be within 6 hours of the subject's scheduled morning dose, the subject should withhold their morning dose of study drug and the morning dose will be administered in the clinic.
 - If the dose in the clinic will be more than 6 hours after the subject's scheduled morning dose, the subject should take the morning dose at home and the evening dose will be administered in the clinic. In this event, all assessments will be collected relative to the evening dose.
6. Subjects will be instructed to bring all used and unused study drug to the site; study drug will be dispensed at each visit, as appropriate.

